8.1. Sequence of analyses

The following safety interim analyses performed by iSRC are planned:

First one will be done once 60 subjects complete one month after first vaccination (i.e., the first 60 subjects completed Visit 2-Day 31)

Second one will be done once 60 subjects complete one month after second vaccination (i.e., the first 60 subjects completed Visit 4- Day 91)

Third one will be done once 300 subjects complete one month after first vaccination (i.e., the first 300 subjects completed Visit 2- Day 31)

Fourth one will be done once 300 subjects complete one month after second vaccination (i.e., the first 300 subjects completed Visit 4- Day 91)

Table 9 Sequence of analyses

Description	Analysis ID	Disclosure Purpose (CTRS=public posting, SR=study report, internal)	Dry run review needed (Y/N)	Study Headline Summary (SHS)requiring expedited communication to upper management (Yes/No)	Reference for TFL
60 subj safety post dose 1	E1_02	Internal	N	N	See SRT column in TOC
60 subj safety post dose 2	E1_03	Internal	N	N	See SRT column in TOC
300 subj safety post dose 1	E1_04	Internal	N	N	See SRT column in TOC
300 subj safety post dose 2	E1_05	Internal	N	N	See SRT column in TOC
All data analysis	E1_01	Study report	Y	Y	All tables in final TOC

CONFIDENTIAL

207489 (NTHI MCAT-002)

Statistical Analysis Plan Amendment 2 FDA Final Draft

8.2. Statistical considerations for interim analyses

Four (unblinded) interim analyses to evaluate the safety during the exposure period will be conducted. These analyses will be performed by an internal Safety Review Committee (iSRC) and study team will not be part of the vaccine unblinded review of safety data.

The iSRC will conduct *unblinded* reviews of all available safety data from the present study while taking into account any other findings that could have an impact on the safety of the subjects and will determine whether there is a safety signal that needs to be escalated to GSK Biologicals' Vaccines Safety Monitoring Board (VSMB). In the event that a safety signal is observed, GSK Biologicals' VSMB might decide to suspend, modify or continue the conduct of the study.

Before each iSRC safety evaluation in this study, the SRT will review the same safety data, but in a ***blinded*** manner.

In addition to the planned iSRC (and SRT) evaluations, *ad hoc* safety evaluations can take place if a safety concern is identified by an investigator or by the SRT.

Interim analysis unblinded data will not be circulated outside of the iSRC team and no individual clinical study report will be written as a result of these safety evaluations.

The planned interim analyses are only for safety monitoring. No conclusions on efficacy, immunogenicity or other endpoints will be carried out, thus no alpha adjustment will be performed.

9. CHANGES FROM PLANNED ANALYSES

Not applicable.

10. LIST OF FINAL REPORT TABLES, LISTINGS AND FIGURES

The TFL TOC provides the list of tables/listings and figures needed for the study report. It also identifies the tables eligible for each analysis and their role (synopsis, in-text, post-text, CTRS). Note that all TFL aimed to be included as post-text are noted as post-text even if these are tabulation of individual data such as listing of SAE. The post-text material contains all source material for the study report and accordingly a post-text table may be redundant with an in-text table.

CONFIDENTIAL

207489 (NTHI MCAT-002)

Statistical Analysis Plan Amendment 2 FDA Final Draft

The standardised asymptotic two-sided 95% CI for the group difference in proportions is based on the method described in the paper from Robert G. Newcombe [[Newcombe, 1985](#)]: interval estimation for the difference between independent proportions: comparison of eleven methods. The standardised asymptotic method used is the method six.

11.2. Standard data derivation

11.2.1. Date derivation

- SAS date derived from a character date: In case day is missing, 15 is used. In case day & month are missing, 30 June is used.
- Onset day for an event (AE, medication, vaccination, ...): The onset day is the number of days between the last study vaccination & the onset/start date of the event. This is 1 for an event starting on the same day as a vaccination. See SAS date derived in case the start date of the event is incomplete.
- Duration: Duration of an event is expressed in days. It is the number of days between the start & the stop dates + 1. Therefore duration is 1 day for an event starting & ending on the same day.

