4.2. Secondary endpoints

Safety:

- Occurrence of each solicited local AE, during the 7-day follow-up period (Day 1 - Day 7) following each vaccination.
- Occurrence of each solicited general AE, during the 7-day follow-up period (Day 1 - Day 7) following each vaccination.
- Occurrence of any unsolicited AE, during the 30-day follow-up period (Day 1 - Day 30) following each vaccination.
- Occurrence of any pIMD from first vaccination up to study conclusion.
- Occurrence of any SAE from first vaccination up to study conclusion.

Efficacy: All AECOPD

- Yearly rate of all AECOPD (any cause, any severity) starting 1 month post-Dose 2, in vaccinated and control subjects.
 - Rate of moderate and severe AECOPD cases in vaccinated and control subjects, during 3, 6 and 9 months observation starting 1 month post-Dose 2.
 - Rate of all AECOPD cases in vaccinated and control subjects, during 3, 6, 9 and 12 months observation starting 1 month post-Dose 2.
 - Rate of all AECOPD cases in vaccinated and control subjects, during 3, 6, 9 and 12 months observation starting 1 month post-Dose 2, by severity.
- Time to first moderate or severe AECOPD.
- Time to first AECOPD of any severity.
- Time to first AECOPD, by severity.
- Duration of moderate and severe AECOPDs.
- Duration of AECOPDs of any severity.
- Duration of AECOPDs, by severity.

CONFIDENTIAL

207489 (NTHI MCAT-002)

Statistical Analysis Plan Amendment 2 FDA Final Draft

Efficacy: AECOPD associated to bacteriological pathogens (PCR)

- Rate of NTHi-associated and/ or Mcat-associated moderate and severe AECOPD, over a period starting 1 month post-Dose 2 and lasting for 1 year.
- Rate of NTHi-associated and/ or Mcat-associated any severity AECOPD, over a period starting 1 month post-Dose 2 and lasting for 1 year.
- Rate of NTHi-associated and/ or Mcat-associated AECOPD, over a period starting 1 month post-Dose 2 and lasting for 1 year, by severity.
- Time to first moderate or severe NTHi-associated and/ or Mcat-associated AECOPD.
- Time to first NTHi-associated and/or Mcat-associated AECOPD of any severity.
- Time to first NTHi-associated and/or Mcat-associated AECOPD, by severity.
- Duration of moderate and severe NTHi-associated and Mcat-associated AECOPD.
- Duration of NTHi-associated and/or Mcat-associated AECOPDs of any severity.
- Duration of NTHi-associated and/or Mcat-associated AECOPD, by severity.

Immunogenicity and CMI:

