The original verbatim terms used by investigators to identify adverse events in the e-CRFs will be mapped to preferred terms using the MedDRA dictionary. The unsolicited adverse events will then be grouped by MedDRA preferred terms into frequency tables according to system organ class. Adverse events judged by the investigator as at least possibly related to study vaccine will be summarized by vaccine group, according to system organ class (SOC) and preferred term within SOC. When an unsolicited adverse event occurs more than once for a subject, the maximal severity and strongest relationship to the vaccine group will be counted.

CONFIDENTIAL

207489 (NTHI MCAT-002)

Statistical Analysis Plan Amendment 2 FDA Final Draft

The percentage of subjects/doses with at least one report of unsolicited AE classified by the Medical Dictionary for Regulatory Activities (MedDRA) during a 30-day follow-up period after each dose (Day 1 –Day 30) will be tabulated with exact 95% CI for each group. The same tabulation will be performed by severity, and for unsolicited AEs with a relationship to vaccination.

SAEs, death, pIMDs and AE leading to withdrawal reported during the entire study will be tabulated (from Day 1 until study termination) and listed.

In addition, SAEs related to study participation or concurrent GSK medication/vaccine reported from informed consent signed until entire study duration will be also listed.

This study foreseen two injections (i.e., two vaccinations) for each subject, and thus unsolicited AEs summary tables will be presented overall and by period of onset and will include frequency distributions of the different adverse events:

Number and percentage of subjects with the following AEs will be computed:

Onset between day 1 and Day 30 after each vaccination:

- Any AE after each vaccination (overall)
- Any AE after each vaccination, by vaccination
- By severity AE after each vaccination (overall)
- By AE severity after each vaccination, by vaccination
- Related unsolicited AEs after each vaccination (overall)
- Related unsolicited AEs after each vaccination by vaccination
- Related unsolicited AEs by severe after each vaccination (overall)
- Related unsolicited AEs by severe after each vaccination by vaccination
- Any medically attended unsolicited AE (overall).
- Any medically attended unsolicited AE, by vaccination

Onset between day 1 and Day 450 (study termination):

- Any serious adverse events (SAE) (overall).

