11.2.2. Dose number

- The study dose number is defined in reference to the number of study visits at which injection occurred. More specifically dose 1 refers to all injections administered at the first vaccination visit (Visit 1) while dose 2 corresponds to all injections administered at the second vaccination visit (Visit 3) even if this is the first time a product is administered to the subject.
- Relative dose: the relative dose for an event (AE, medication, vaccination) is the most recent study dose given before an event. In case the event takes place on the day a study dose is given, the related dose will be that of the study dose, even if the event actually took place before vaccination. For instance, if an adverse event begins on the day of the study vaccination but prior to administration of the vaccine, it will be assigned to this dose.
- The number of doses for a product is the number of time the product is administered to a subject.
- The incidence per dose is the number of vaccination visits at which an event was reported among all vaccination visits.

CONFIDENTIAL207489 (NTHI MCAT-002)
Statistical Analysis Plan Amendment 2 FDA Final Draft**11.2.3. Demography**

- Age: Age at the reference activity, computed as the number of units between the date of birth and the reference activity. Note that due to incomplete date, the derived age may be incorrect by 1 month when month is missing from the birthdate. This may lead to apparent inconsistency between the derived age and the eligibility criteria/the age category used for randomization.
- Conversion of weight to kg

The following conversion rule is used:

- Weight in Kilogramm= weight in Pounds / 2.2
- Weight in Kilogramm =weight in ounces / 35.2

The result is rounded to 2 decimals.

- Conversion of height to cm

The following conversion rule is used:

- Height in Centimetres = Height in Feet * 30.48
- Height in Centimetres = Height in Inch * 2.54

The result is rounded to the unit (ie no decimal).

- Conversion of temperature to °C

The following conversion rule is used:

- Temperature in °Celsius = ((Temperature in °Fahrenheit -32) *5)/9

The result is rounded to 1 decimal.

- Smoking status

Subjects reporting smoking status START DATE='Before' and STOP DATE='Before' will have value 'Former' (i.e., no smoker)

Subjects reporting smoking status START DATE='Before' and STOP DATE='Ongoing' will have value 'Current' (i.e., smoker)

- Exacerbations in previous 12 months

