11.2.6. Safety

Solicited adverse event: With the exception of 60 minutes after vaccination, solicited adverse events are collected via e-diary and thus no DCF (data clarification form) will apply in case of inconsistency reporting.

CONFIDENTIAL

207489 (NTHI MCAT-002)

Statistical Analysis Plan Amendment 2 FDA Final Draft

For a given subject and the analysis of solicited adverse events within 7 days post-vaccination, missing or non-evaluable measurements will not be replaced. Therefore the analysis of the solicited adverse events based on the Total Vaccinated Cohort (TVC) will include only vaccinated subjects for doses with documented safety data (i.e., symptom screen completed). More specifically the following rules will be used:

- Subjects who documented the absence of a solicited symptom after one dose will be considered not having that symptom after that dose.
- Subjects who documented the presence of a solicited symptom and fully or partially recorded daily measurement over the solicited period will be included in the summaries at that dose and classified according to their maximum observed daily recording over the solicited period.
- Subjects who documented the presence of a solicited symptom after one dose without having recorded any daily measurement will be assigned to the lowest intensity category at that dose (i.e., 37.5°C for fever or grade 1 for other symptoms).
- Doses without symptom sheets documented will be excluded.
- All solicited adverse events will be considered probably related to study vaccine.

Unsolicited adverse events: For analysis of unsolicited adverse events, such as serious adverse events or adverse events by primary MedDRA term, and for the analysis of concomitant medications, all vaccinated subjects will be considered. Subjects who did not report the adverse event or the concomitant medication will be considered as subjects without the event or the concomitant medication respectively.

- Unsolicited AE will be classified in the e-CRF as possibly related to study vaccine (YES or NO), based on the PI judgment.
- The related dose for an event (e.g., AE, medication, vaccination,...) is the study dose given before an event. In case the event takes place on a day a study dose is given, the related dose will be that of the study dose even if the event actually took place before. For instance, for a conc. medication started on the day of study dose 2 but before dose 2 administrations, the related dose will be dose 2.

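### Partial adverse-event onset dates are imputed without reference to the dose date, so some events after vaccination are dated before the dose or misattributed between doses

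*SAP*

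**What the plan says.** The current SAP (Amendment 2), section 11.2.1, fixes incomplete dates as follows: "In case day is missing, 15 is used. In case day & month are missing, 30 June is used". The onset-day rule in the same section applies this to events: "See SAS date derived in case the start date of the event is incomplete". It counts from the last dose: "The onset day is the number of days between the last study vaccination & the onset/start date of the event", with the dose day as Day 1. Section 11.2.2 attributes events in the same way: "the relative dose for an event (AE, medication, vaccination) is the most recent study dose given before an event". The only special case, in sections 11.2.2 and 11.2.6, is an event on the dose day itself, which is given to that dose even if it began beforehand.

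The secondary safety endpoint in section 4.2 is "Occurrence of any unsolicited AE, during the 30-day follow-up period (Day 1 - Day 30) following each vaccination", and the unsolicited AE tables in section 6.5.1.2 select "Onset between day 1 and Day 30 after each vaccination". SAEs, pIMDs and AEs leading to withdrawal are tabulated from Day 1 to Day 450. For unsolicited events, Table 10 keeps every vaccinated subject in the denominator, and section 11.2.6 adds: "Subjects who did not report the adverse event or the concomitant medication will be considered as subjects without the event".

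**The concern.** The imputed date decides whether an event is counted and to which dose it belongs, yet the imputation ignores when the dose was given. An event known to have begun in the dose month, and possibly after the injection, can be placed before vaccination by arithmetic alone. A subject whose only event is misdated in this way stays in the denominator and leaves the numerator, so the table shows no sign of it. The plan resolves doubt on the dose day towards the dose, whereas this rule can do the opposite for an event a few days later. At stake are the percentages in the 30-day unsolicited AE tables and their split by vaccination.

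**Working it through.** The SAP gives no figure on this point, so there is none to reproduce. The check applies the stated rule to every combination of dose date and true onset.

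**Inputs.** From the SAP: missing day set to the 15th; missing day and month set to 30 June; dose day = Day 1; window Day 1–30; Dose 2 on Day 61. Assumed: dose dates and onset days are uniform. The share of events with partial dates is unknown and is not assumed.

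**Examples.**
- Dose 20 March, onset 24 March (Day 5), day missing: imputed 15 March, five days before the dose.
- Dose 1 on 20 March, Dose 2 on 19 May, onset 22 May (Day 4 of Dose 2): imputed 15 May, which is Day 57 of Dose 1 and outside both windows.
- Dose 5 October, onset 2 November (Day 29): imputed 15 November, Day 42.

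**Losses, 30-day months.** There are 30 dose days × 30 onset days = 900 true in-window cases. Let *d* be the day of the month on which the dose is given.
- Dated before the dose (*d* ≥ 16, onset later in the same month): Σ(31 − *d*) for *d* = 16 to 30 = 15 + 14 + … + 1 = 120, or 13.3%.
- Dated after Day 30 (*d* ≤ 15, onset in the next month, imputed day 46 − *d* > 30): Σ(*d* − 1) for *d* = 1 to 15 = 105, or 11.7%.

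**Gains in the same model**, at the same density of events outside the window:
- True onset after Day 30 but dated inside (*d* ≥ 16, onset in the next month): Σ(31 − *d*) = 120.
- True onset before the dose but dated inside (*d* ≤ 15, onset earlier in the same month): Σ(*d* − 1) = 105.

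Losses and gains are both 225.

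**Calendar year** (365 dose dates × 30 onset days = 10,950):

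| Missing | Dated before dose | Dated after Day 30 | Stays in window |
|---|---|---|---|
| Day | 1,523 (13.9%) | 1,260 (11.5%) | 8,167 (74.6%) |
| Day and month | 5,085 (46.4%) | 4,965 (45.3%) | 900 (8.2%) |

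In the day-missing row the gains again offset the losses: 1,523 events from after Day 30 and 1,260 from before the dose.

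**Dose 2.** The 15th lies 1 to 16 days before a dose given on the 16th to the 31st. With Dose 2 on Day 61, that is Day 45 to Day 60 of Dose 1. On schedule, all of the 13.9% therefore leave both 30-day windows.

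**Day 1–450 tables.** With onset uniform over Day 1–450, the share dated before Dose 1 is about 0.9% when the day is missing and 10.4% when day and month are missing.

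**The case against.** Mid-period imputation is meant to be neutral, and under uniform timing it is: as many events enter the window as leave it. A reader might infer from 13.3% + 11.7% that a quarter of partially dated events are lost and that safety is understated by that amount. The documents do not support this. The offset does depend on events outside the window being recorded. Section 6.5.1.2 says that all unsolicited AEs during the study are recorded, but the shading of Table 4 that would confirm it is not legible. If no pre-dose events are recorded at Dose 1, the net loss there is 225 − 120 = 105 of 900 (11.7%), still not one in four.

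A reader might also infer that SAEs and pIMDs drop out widely. They do not: an event misdated before Dose 2 stays in the overall Day 1–450 tables under Dose 1, and section 6.5.1.2 also requires these events to be listed. Nor is a bias between arms shown, since one rule serves both arms of an observer-blind trial and the safety analysis is descriptive.

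Partial dates are probably few. Unsolicited AEs are entered in the e-CRF, and the SAP rules out data clarification only for e-diary solicited events. Visits on Days 31, 61 and 91 make a wholly missing month unlikely for an in-window event. Solicited AEs, collected by e-diary, are hardly touched.

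All of this limits the weight of the point. What remains is that a rule the SAP itself states can date a post-dose event before vaccination when the known month and year do not require it.

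**Conclusion.** The point holds as a minor defect in a derivation rule. Among true Day 1–30 events with a missing day, about 13–14% would be dated before the dose and about 11.5% after Day 30, with movement into the window in the other direction. These shares are conditional on a partial date and on uniform timing; risk concentrated soon after a dose would change them and break the exact offset. The absolute effect cannot be computed, because the number of partial dates is not given. It falls mainly on the 30-day unsolicited AE tables and on attribution by dose. In the Day 1–450 tables only dates before Dose 1 are lost. No efficacy result is involved.

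**What to change.** Keep the mid-period rule and add one sentence to section 11.2.1 for AE onset. If the imputed date falls before a study dose given in the same known month and year (or, for year-only dates, before Dose 1 in that year), set onset to that dose date, unless the stop date or other recorded data show that the event began or ended before the dose.

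In the 30-day-month model with the day missing, this returns the 120 pre-dose losses to the window and leaves the 105 dated after Day 30 as they are.

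The cost is not nil. Events that truly began earlier in the Dose 2 month, with nothing recorded to show it, will be counted under Dose 2. At uniform density this adds Σ(*d* − 1) for *d* = 16 to 30 = 330 to the 105 already drawn in, if such events are recorded. Some later year-only events will enter the Dose 1 window. Both errors run in the conservative direction for safety.

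A broader rule that sets every other month to its first day is not advised. It would draw in Σ(31 − *d*) for *d* = 2 to 30 = 435 true post-Day-30 events, against 120 now. Reporting the number of imputed onset dates by group would show whether any of this matters.

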11.2.2. Dose number

- The study dose number is defined in reference to the number of study visits at which injection occurred. More specifically dose 1 refers to all injections administered at the first vaccination visit (Visit 1) while dose 2 corresponds to all injections administered at the second vaccination visit (Visit 3) even if this is the first time a product is administered to the subject.
- Relative dose: the relative dose for an event (AE, medication, vaccination) is the most recent study dose given before an event. In case the event takes place on the day a study dose is given, the related dose will be that of the study dose, even if the event actually took place before vaccination. For instance, if an adverse event begins on the day of the study vaccination but prior to administration of the vaccine, it will be assigned to this dose.
- The number of doses for a product is the number of time the product is administered to a subject.
- The incidence per dose is the number of vaccination visits at which an event was reported among all vaccination visits.

CONFIDENTIAL207489 (NTHI MCAT-002)
Statistical Analysis Plan Amendment 2 FDA Final Draft**11.2.3. Demography**

- Age: Age at the reference activity, computed as the number of units between the date of birth and the reference activity. Note that due to incomplete date, the derived age may be incorrect by 1 month when month is missing from the birthdate. This may lead to apparent inconsistency between the derived age and the eligibility criteria/the age category used for randomization.
- Conversion of weight to kg

The following conversion rule is used:

- Weight in Kilogramm= weight in Pounds / 2.2
- Weight in Kilogramm =weight in ounces / 35.2

The result is rounded to 2 decimals.

- Conversion of height to cm

The following conversion rule is used:

- Height in Centimetres = Height in Feet * 30.48
- Height in Centimetres = Height in Inch * 2.54

The result is rounded to the unit (ie no decimal).

- Conversion of temperature to °C

The following conversion rule is used:

- Temperature in °Celsius = ((Temperature in °Fahrenheit -32) *5)/9

The result is rounded to 1 decimal.

- Smoking status

Subjects reporting smoking status START DATE='Before' and STOP DATE='Before' will have value 'Former' (i.e., no smoker)

Subjects reporting smoking status START DATE='Before' and STOP DATE='Ongoing' will have value 'Current' (i.e., smoker)

- Exacerbations in previous 12 months

Data will be categorized as following:

1. AECOPDs in the last 12 months managed without oral corticosteroids and antibiotics ='Mild'
2. AECOPDs in the last 12 months that required oral corticosteroids and/or antibiotics ='Moderate'
3. AECOPDs in the last 12 months that required hospitalization='Severe'

CONFIDENTIAL207489 (NTHI MCAT-002)
Statistical Analysis Plan Amendment 2 FDA Final Draft**11.2.4. Efficacy**

- **AECOPD events:** AECOPD events are confirmed according to investigator judgment after an AECOPD visit which is aimed to exclude worsening in symptoms not related to an AECOPD event.

eDiary alerts refer to daily symptoms recorded the morning after (also called morning symptoms). Alerts are based on the Anthonisen criteria:

- Worsening of two or more of the following major symptoms for at least two consecutive days*: dyspnea, sputum volume, sputum purulence (color)
Or
- Worsening of any major symptom together with any of the following minor symptoms for at least two consecutive days*: sore throat, cold (nasal discharge and/or nasal congestion), fever (oral temperature $\geq 37.5^{\circ}\text{C}$) without other cause, increased cough, increased wheeze.

* *The same two symptoms do not have to be present on both days as long as at least one major symptom is present on both days.*

AECOPD visits are scheduled after an electronic Diary Card alert confirmed by the investigator (by phone call or at the study site) or after spontaneous site visits due to worsening symptoms without any alert.

[figure not shown]
Potential AECOPD will be confirmed and registered as AECOPD event based on the following scheme:

- eDiary ALERT + phone call no confirmed = NO AECOPD event
- eDiary ALERT + phone call confirmed + site visit confirmed = AECOPD event.
- eDiary ALERT + phone call confirmed + site visit no confirmed = NO AECOPD event.
- eDiary ALERT + phone call confirmed + site visit no performed + Medical record confirmed = AECOPD event.
- eDiary ALERT + phone call confirmed + site visit no performed + Medical record no confirmed = NO AECOPD event.
- eDiary ALERT + phone call confirmed + site visit NO performed + Medical record no available = AECOPD event.
- eDiary NO ALERT + site visit NO confirmed = NO AECOPD event.
- eDiary NO ALERT + site visit confirmed = AECOPD event.
- eDiary NO ALERT + site visit NO performed + Medical record confirmed = AECOPD event.
- eDiary NO ALERT + site visit NO performed + Medical record no available/no confirmed = NO AECOPD event

CONFIDENTIAL

207489 (NTHI MCAT-002)

Statistical Analysis Plan Amendment 2 FDA Final Draft

Figure 3 AECOPD assessment*

*Only AECOPD confirmed by the Investigator and reported in eCRF will be counted for efficacy analysis.

- **AECOPD onset date:** AECOPD onset is defined as the first day of the two consecutive days of worsening symptoms and it entered in e-CRF by the investigator.
- **AECOPD recovery date:** AECOPD recovery will be determined / confirmed by the investigator during (a) follow-up phone call(s) which will take place every 2 weeks until the AECOPD has resolved. The end date should be based on when the investigator and/or subject determines that the AECOPD symptoms have returned to pre-exacerbation levels or to a new baseline. In determining this end date, consideration will be given to symptoms recorded in the electronic Diary Card and patient assessment during the phone calls.
- **AECOPD duration** will be defined as the number of days from AECOPD onset (included) and AECOPD recovery (not included).

$$\text{Duration} = \text{date2} - \text{date1},$$

with date2: AECOPD recovery date,
date1: AECOPD onset date
- **Unconfirmed AECOPD event with morning e-diary signal alert notification:** An alert from the electronic Diary Card not confirmed to be an AECOPD after contact by phone call or at the study site.

CONFIDENTIAL

207489 (NTHI MCAT-002)

Statistical Analysis Plan Amendment 2 FDA Final Draft

- **Grading of severity of an exacerbation:** Severity of exacerbations is defined as per protocol:
 - Mild: Worsening symptoms of COPD that are self-managed by the patient.
 - Moderate: Worsening symptoms of COPD that require treatment with oral corticosteroids and/or antibiotics.
 - Severe: Worsening symptoms of COPD that require treatment with in-patient hospitalisation or home care intervention.

Severity of the exacerbation will not be derived but taken directly from the information entered in the CRF (i.e. Severity of exacerbation will be taken from the conclusion of the exacerbation visit).

